2.1 Number, Gender, Age and Racial/Ethnic Origin of Subjects

2.1.1 Number

It is expected that approximately 45 participants will be enrolled at NYU Langone Medical Center in order to produce 30 eligible participants at this site. Approximately 45 participants will also be enrolled at Nathan Kline Institute to produce 30 evaluable participants at that site. Participants enrolled at NYU will primarily be recruited from flyers throughout the NYU campus, internet advertisements, newspaper advertisements, recruitment emails to university mailing lists and previous studies from prior studies conducted by the lab and will directly contact the Research Coordinator for more information.

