4.2 Data Analysis and Data Monitoring

(See R21/R33 application for section references)

The primary endpoints of the study are clinical symptoms and fMRI data. The specific analyses (independent and dependent variables) will be unique to each task, as described below. Safety and tolerability of 4 weeks of 24 mg ondansetron will also be evaluated.

Alpha level will be set at 0.05 for all analyses. Task-based fMRI analysis will focus on brain activation in an a priori ROI consisting of bilateral insula and somatosensory cortex, although exploratory whole-brain analyses will also be conducted. Primary group-level analyses for the R33 phase will be performed on a modified intent to treat sample consisting of participants completing at least 2 weeks of treatment. Missing data values are expected to amount to 10% or less of the data. We will consider them as MAR and impute based on a regression model. The degrees of freedom of t-tests will be adjusted appropriately. Secondary per-protocol analyses will also be conducted.

Task-based and symptoms analyses for R33:

First-level fMRI analysis: For each fMRI task, image analysis at the first (subject) level will specify separate regressors for baseline and week 4 for conditions of interest (e.g., for the "urges-for-action" task: blink suppression at baseline, blink suppression at week 4, rest at baseline, rest at week 4) to examine contrasts between baseline and week 4 (e.g., blink suppression vs. rest for baseline vs. week 4). For each task, contrasts will also examine activation during the baseline scan only (e.g., blink suppression vs. rest at baseline scan). These latter contrasts will be performed in order to measure and adjust for any baseline differences in ROI activation between ondansetron and placebo groups.

Group-level fMRI analysis: Testing for Hypothesis 2: Two-sample t-tests will compare ondansetron and placebo groups on change in activation over the 4-week trial (using first-level contrasts comparing baseline with week 4). However, if there are significant baseline differences between the groups within the insula and somatosensory ROI (using two-sample t-tests on baseline scan contrasts), standardized parameter estimates will be extracted from these regions for each subject. These parameter estimates will then be specified as covariates in follow-up one-way ANOVAs comparing ondansetron and placebo groups on change in activation from baseline to week 4 after adjusting for baseline differences.

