Relationships with clinical symptoms: Testing for Hypothesis 3a: A change score will be computed between SPS score at baseline and after 4 weeks for each subject. Two-sample t-tests will compare ondansetron and placebo groups on SPS change scores to determine whether the intervention reduces SP significantly more than placebo. In addition, change scores from baseline to week 4 will be computed for measures of overall symptom severity (using Y-BOCS and YGTSS) and compared between ondansetron and placebo groups. If there are baseline differences between the groups in any of the symptom scales (SPS, Y-BOCS, or YGTSS), follow-up one-way ANOVAs will compare change scores between ondansetron and placebo groups after adjusting for baseline scores. Testing for Hypothesis 3b: If there are significant differences between ondansetron and placebo groups in (1) SPS change scores and (2) Y-BOCS or YGTSS change scores, a Sobel test of mediation 205, 206 will investigate whether group differences in Y-BOCS/YGTSS changes are mediated by SPS changes. Briefly, mediation analyses perform a series of regressions in order to determine whether the relationship between an independent and dependent variable (e.g., treatment group and Y-BOCS/YGTSS scores) reduces significantly after including a third mediator variable (e.g., SPS score). Testing for Hypothesis 3c: If there are significant differences between ondansetron and placebo groups in (1) SPS change scores and (2) change in ROI activation or connectivity from baseline to week 4, a Sobel test will investigate whether group differences in SPS change are mediated by changes in activation or connectivity.

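### Regression imputation with only a degrees-of-freedom adjustment does not guarantee the 0.05 level for the symptom t-tests: if imputation is single, error is about 5-8% at 10% missing, or the effect is diluted 6-10%

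*Combined protocol and SAP*

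**What the plan says.** All of the missing-data plan stands in section 4.2, Data Analysis and Data Monitoring. It sets the level ("Alpha level will be set at 0.05 for all analyses"), the expected loss ("Missing data values are expected to amount to 10% or less of the data"), the method ("We will consider them as MAR and impute based on a regression model") and the correction ("The degrees of freedom of t-tests will be adjusted appropriately").

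The primary group-level set is a "modified intent to treat sample consisting of participants completing at least 2 weeks of treatment". A patient who stops after week 2 is therefore in the set and may have no week-4 value.

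Hypothesis 3a is tested on week-4 change: "Two-sample t-tests will compare ondansetron and placebo groups on SPS change scores". Y-BOCS and YGTSS change scores are compared between groups as well. For Hypothesis 2, "Two-sample t-tests will compare ondansetron and placebo groups on change in activation over the 4-week trial".

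Section 4.2 does not say whether imputation is single or multiple, whether a random residual is added, which predictors enter, whether arm is one of them, or how the degrees of freedom are to be adjusted. No other section says so either.

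**The concern.** An imputed value adds no information about the treatment difference beyond what the observed data hold. If each gap is filled once and the completed data are analysed as if observed, the standard error is too small for two reasons: the sample is counted as larger than it is, and values placed on a regression line add no residual scatter. A smaller degrees-of-freedom figure in the t table acts on neither.

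The direction of harm depends on a choice left open. With arm in the imputation model the error is in the standard error. With arm out, imputed values carry no treatment difference, so the estimate is pulled towards zero.

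This touches the primary symptom comparisons. It also carries forward, because section 4.2 opens the mediation tests of Hypotheses 3b and 3c only when group differences are significant.

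**Working it through.** **Inputs from the plan.** Level 0.05 (two-sided assumed). Missing values at most 10% (section 4.2), taken here as the share missing at week 4. Section 2.1.1 aims "in order to produce 30 eligible participants at this site" and another 30 at the second site, so 60. The allocation ratio is not given; 30 per arm is assumed. The plan gives no power calculation, SD or correlation, so its only figure to test against is 0.05. Correlations below are assumptions.

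**Closed form, arm as the only predictor.** Each arm has 30 patients, 27 observed and 3 filled with the arm mean. The filled values leave the sum of squares SS and the mean difference unchanged.

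- Honest variance of the difference: SS/52 × 2/27.
- Variance reported on the completed data: SS/58 × 2/30.
- The t statistic is inflated by √(58/52 × 30/27) = √1.239 = 1.113.
- Degrees of freedom left at 58: 2.0017/1.1132 = 1.798, and P(|t52| > 1.798) = 7.8%.
- Reduced to 52 in the critical value only: 2.0066/1.1132 = 1.803, giving 7.7%.
- Reduced to 52 in the critical value and the pooled variance: inflation is √(30/27) = 1.054, 2.0066/1.0541 = 1.904, giving 6.2%.

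Changing the critical value alone moves the error by less than 0.1 point. Arm size matters little: with 20 per arm (2 filled, 34 df) the last two figures are 7.7% and 6.2%; with 10 per arm (1 filled, 16 df), 7.6% and 6.1%. Y-BOCS and YGTSS are given to OCD and tic patients respectively, so each has fewer than 30 per arm.

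**Simulation.** 30 per arm, 10% of week-4 values deleted at random, deterministic single imputation with arm in the model, t-test on change, 20,000 to 60,000 runs per setting:

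| Predictors besides arm | Reduced df in critical value only | Reduced df also in pooled variance |
|---|---|---|
| none | 7.7-7.9% | 6.2-6.5% |
| baseline (correlation with week 4 from 0.3 to 0.9) | 6.7-7.6% | 5.3-6.1% |
| baseline, week 2 | 6.1-6.3% | 4.8-5.1% |
| baseline, weeks 1-3 | 5.9% | 4.7% |

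Adding a random residual to each imputed value (baseline and week 2) still gives 6.1% in the first column. At 5% missing, the figures are 6.1% (arm and baseline) to 6.3% (arm alone) in the first column and 5.4-5.5% in the second.

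**Arm left out.** With no predictor, or baseline only, imputed values have the same expectation in both arms, so the expected difference is 0.9 of the true one: 0.9 × 0.60 = 0.54 SD and 0.9 × 0.50 = 0.45 SD. Simulation agrees. With baseline and week 2, 0.74 SD becomes 0.69, and 0.69/0.74 = 0.93, a loss of about 6%. Type I error is 4.6-5.0%, or 3.5-3.9% with reduced df in the variance. Power is hardly affected relative to complete cases (77% against 76% at 0.74 SD), so the cost is bias in the estimate.

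**Comparators at 10% missing.** Multiple imputation (20 sets, arm in the model, Rubin's rules, Barnard-Rubin df): 4.6-5.0%. Complete-case t-test: 4.9%.

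**The case against.** A reader might infer that the primary p-values are simply too small, at about 7% false positives. The documents do not support that as a flat statement, for four reasons.

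- **Multiple imputation is not excluded.** Regression is a standard imputation model within it, and adjusted degrees of freedom belong to it. On that reading the error is about 5%. This stands, and makes the finding conditional. But the plan names neither multiple imputation nor a combining rule, so the text needs changing either way.
- **A degrees-of-freedom adjustment can do more than move the critical value.** In a pooled t-test the same number divides the sum of squares. Used in both places it brings the error to 5-6.5%, and to about 5% with interim scores as predictors. This also stands. The plan does not say which use is meant or whether interim scores enter.
- **10% is a ceiling on all data, not an estimate for week 4.** At 5% missing the excess is about 1 point. One could argue the other way, that losses collect at week 4 and push its share above 10%. The plan does not say so, and the 2-week rule removes earlier dropouts from the set.
- **Hypothesis 2 may not be affected.** A reader might extend these figures to the scan contrasts, since they are also t-tests. The plan does not say that scans will be imputed, its resting-state text excludes high-motion subjects without mentioning imputation, and the calculation covers a single score at two visits, not imaging data. The figures should not be carried over.

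**Conclusion.** The concern holds in conditional form. Section 4.2 imputes from a regression model and names one correction, which does not by itself carry imputation uncertainty.

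Under single imputation, 30 per arm and 10% missing at week 4, the symptom t-tests run at about 6-8% with arm in the model and only the critical value adjusted, or about 5-6.5% with the pooled variance adjusted too. With arm omitted the level holds but the effect is understated by about 6-10%. Under multiple imputation there is no error in level, only an unnamed method. The result rests on assumed equal allocation, assumed correlations and values lost at random.

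The size is modest. The case for acting is that the plan leaves open which of these outcomes applies, so the choice could be made after the data are seen.

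**What to change.** Replace the two sentences on imputation and degrees of freedom with the following.

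- **SPS, Y-BOCS and YGTSS:** multiple imputation of missing scores, with treatment arm, baseline and the scores from about days 7, 14 and 21 in the model, each scale among the patients rated on it. State the number of imputed sets. Combine the t-test results by Rubin's rules, using the degrees of freedom those rules supply (for example Barnard-Rubin).
- **Scans:** the analysis uses patients with both the baseline and the week-4 scan, with no imputation. Report the number excluded per arm and why.

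Section 4.1 already collects the interim scores and section 5 already lists SAS, so no visit or measurement is added. The downside is slightly wider confidence intervals and a little more analysis work.

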2.2 Inclusion Criteria

Criteria for all participants

- Ages between 18 and 60 years
- Fluent (speaking and writing) in English.
- Diagnosis of obsessive-compulsive disorder (OCD) or tic disorder (OCD) according to DSM-5 criteria as determined with the Mini International Neuropsychiatric Interview (MINI, Sheehan et al., 1998; J Clin Psychiatry, 59 Suppl 20, 22-33)
- Moderate or greater disorder severity: ≥ 16 on the Yale-Brown Obsessive Compulsive Scale (Y-BOCS) or ≥ 20 on the Yale Global Tic Severity Scale (YGTSS)
- Moderate or greater severity of sensory phenomena (≥ 6 on the Sensory Phenomena Scale, SPS)
- Stable on psychotropic medication for at least 6 weeks or unmedicated.

Additional criteria for all participants who are screened remotely

access to a computer or phone with a camera

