- 2. Psychiatric and Symptom Evaluation (90-180 minutes): If consent is acquired, we will perform a longer screening for psychiatric history using the Mini International Neuropsychiatric Interview (M.I.N.I., Sheehan et al. 1998). This tool contains diagnostic modules for the assessment of several psychiatric conditions including mood, substance use, anxiety, psychotic, and eating disorders. The Columbia-Suicide Severity Rating Scale (C-SSRS; Posner et al., 2011) will be used to determine risk for suicide. Sensory phenomena will be assessed using the Sensory Phenomena Scale (SPS, Rosario et al., 2009). This semi-structured scale assesses the presence and severity of different types of SP preceding or occurring at the same times as repetitive behaviors in OCD. The SPS contains a checklist with examples of different types of SP encompassing all previous descriptions in the literature, including physical sensations, "just right" sensations, incompleteness, general energy or inner tension buildup, and urges. OC symptoms in OCD patients will be assessed using the Yale-Brown Obsessive Compulsive Scale (Y-BOCS, Goodman et al., 1989), while tics symptoms in TD patients will be assessed using Yale Global Tic Severity Scale (YGTSS, Leckman et al., 1989). Psychiatric symptoms including suicidality will be confirmed by a licensed clinician on the protocol to ensure participant safety. If the clinician determines that the subject is at an immediate and significant health risk, they will be sent to the nearest Emergency Department. If the visit is conduted remotely via videoconferencing and no study clinician is available at that moment to speak with the participant, a member of the study team will direct the participant to call 911 or go to the nearest psychiatric emergency department. We will also have subjects complete several self-rated scales or questionnaires to assess a variety of other symptoms: Beck Depression and Anxiety Inventories (Beck et al. 1996), Dimensional Obsessive-Compulsive Scale (Abramowitz et al. 2010), Penn State Worry Questionnaire (Meyer et al. 1990), Multidimensional Assessment of Interoceptive Awareness (Mehling et al., 2012), Adolescent/Adult Sensory Profile Scale (Brown and Dunn., 2002), the Perseverative Thinking Questionnaire (PTQ; Ehring et al., 2011), Frost Multidimensional Perfectionism scale (Frost et al., 1990), Obsessive-Compulsive Trait Core Dimensions Questionnaire (Pietrefesa et al., 2009), Resilience Scale (Wagnild et al., 1993), Not Just Right Experiences Questionnaire, Revised (Coles et al., 2003), Obsessive-Compulsive Inventory (Foa et al., 1998), Quick Inventory of Depressive Symptomatology (Rush et al., 2003).

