Resting-state functional connectivity analysis: After heart rate and respiratory signals are removed from resting-"RETROICOR"207. analysis will proceed usina (www.nitrc.org/projects/conn) following our previous protocol26. Timecourses of the BOLD signal for each rest scan will be extracted from four seeds (6-mm radius spheres) in bilateral insula (two seeds in anterior and two seeds in mid-posterior insula, coordinates taken from prior work26,208). Partial correlations will be conducted between these timecourses and whole-brain gray matter, controlling for several factors. Timecourses from the top three principle components within white matter and CSF will be determined using the "CompCor" method209 and included as covariates to control for noise without having to regress out global signal210,211. Additionally, the inclusion of 12 motion variables (6 realignment parameters and first derivatives) as covariates will control for movement. Because movement is a major concern for connectivity analysis 212, we will exclude from restingstate analyses any subject moving > 1 mm or 0.5 degrees. Data will be filtered between 0.01 and 0.10 Hz213. At the first level, partial correlation coefficient images between each seed's timecourse and the whole brain will be z-transformed and compared in contrasts between baseline and week 4. For Hypotheses 2 and 3c (R33). two-sample t-tests will compare ondansetron and placebo groups in change in connectivity between baseline and week 4. As with task analyses, baseline differences will be probed using t-tests and included as covariates in follow-up ANOVAs if necessary.

Additional post-hoc analyses: Exploratory whole-brain analyses will be conducted for all contrasts of interest, correcting for multiple comparisons using cluster-level false discovery rate. For the R33 phase, we will probe for correlations between SPS score and whole-brain activation and connectivity in order to identify other future targets for treatment. We will also examine associations between other clinical measures (DOCS, PUTS, GAF)

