and ondansetron treatment as well as brain functioning. Investigation of symptom trajectories over the duration of the trial will use ANOVAs with time (baseline, week 1, 2, 3, 4) as a repeated measure. Any clinical or demographic differences remaining between the groups after randomization including age, gender, illness duration, and medication dosage (using fluoxetine equivalence) will be statistically controlled for in all analyses. For illness duration and medication, follow-up analyses will investigate the relationship between these variables and study measures (brain functioning and symptoms), not only to control for confounding but also to interrogate these variables as factors of interest.

A Data Safety Monitoring Board consisting of external scientists was assembled in August of 2015 for the R21 phase. This DSMB met every 6 months (February, August of 2016, and March 2017) via teleconference to review aggregate safety data. The board will continue to meet at this same schedule during the R33 phase. The DSMB meeting in March 2017 approved continuation to the R33 phase using the procedures described in this protocol. The board last met on December 20, 2017 (6 months after the start of the R33 phase in June of 2017) and approved the continuation of the R33 phase.

- i. The primary safety measure discussed at DSMB meetings is the incidence of adverse events, which are assessed weekly throughout the trial using the Patient-Rated Inventory of Side effects (Rush et al., 2004, Control Clin Trials, 25, 119-142). The PRISE consists of a checklist of side effects in the categories of: Gastrointestinal, Heart, Skin, Nervous System, Eyes/Ears, Genital/Urinary, Sleep, Sexual Functioning, and Other (which includes symptoms related to energy and mood). Patients endorse items and indicate whether they are tolerable or distressing. Secondarily, safety outcomes related to results from medical surveillance tests (EKG, blood test) occurring during Mid-trial and Final visits will be discussed.

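### Baseline should be a pre-specified covariate in every primary comparison, not one added only after an observed imbalance

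*Combined protocol and SAP*

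**What the plan says.** All references are to Section 4.2 (Data Analysis and Data Monitoring) unless noted.

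- **Task fMRI (Hypothesis 2).** The arms are compared by two-sample t-test on change in activation. Adjustment is conditional: "However, if there are significant baseline differences between the groups within the insula and somatosensory ROI (using two-sample t-tests on baseline scan contrasts". Only then are baseline parameter estimates extracted and used as covariates in a follow-up ANOVA of change.
- **Symptom scales (Hypothesis 3a).** SPS change is compared by two-sample t-test, and Y-BOCS and YGTSS change scores are also compared between arms. The condition here is: "If there are baseline differences between the groups in any of the symptom scales (SPS, Y-BOCS, or YGTSS), follow-up one-way ANOVAs". No test or threshold is named.
- **Connectivity.** Change is again compared by t-test; "baseline differences will be probed using t-tests and included as covariates in follow-up ANOVAs if necessary".
- **Other covariates.** These are also chosen from what is observed: "Any clinical or demographic differences remaining between the groups after randomization including age, gender, illness duration, and medication dosage". The outcome's own baseline value is not in that list.
- **Mediation (Hypotheses 3b and 3c).** The Sobel tests are run only after two significant group differences. For 3b: "If there are significant differences between ondansetron and placebo groups in (1) SPS change scores and (2) Y-BOCS or YGTSS change scores".

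Nowhere is adjustment for the outcome's own baseline made unconditional.

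**The concern.** There are three faults.

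1. **Lost precision.** A change score fixes the slope on baseline at 1. Unless the true slope is 1, this leaves baseline noise in the comparison. The plan collects the baseline value and describes a model that uses it, but applies that model only when an imbalance is noticed.
2. **Mis-correction in individual trials.** A moderate chance imbalance that does not trigger adjustment is handled by the change score alone. When the true slope is below 1 this over-corrects.
3. **An analysis chosen by the data, under three different triggers.** The trigger is significance for task fMRI, need for connectivity, and any difference for the scales. For task fMRI it is unclear whether the covariate comes from the whole a priori ROI or only from the parts that differed. Nothing says whether the t-test or the follow-up model decides when they disagree. Two analysts following the text could therefore differ on whether mediation may be tested at all.

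Hypotheses 2 and 3a lose power directly. Hypotheses 3b and 3c each require two significant results, so there the loss compounds.

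**Working it through.** **Inputs from the documents.** Alpha is 0.05 (Section 4.2; two-sided assumed). Section 2.1.1 expects 30 eligible patients at NYU and, for the other site, "Approximately 45 participants will also be enrolled at Nathan Kline Institute to produce 30 evaluable participants at that site". I take the total as about 60, or 30 per arm, assuming 1:1 allocation.

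**Assumed, because the documents give none.** Baseline-to-week-4 correlation ρ of 0.3, 0.5 or 0.7; an effect of 0.6 week-4 SD; several ratios of week-4 to baseline SD. The plan states no power figure to reproduce.

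**Formulas.** With baseline SD σ₀ and week-4 SD σ₁:

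- Var(change) = σ₀² + σ₁² − 2ρσ₀σ₁
- Var(ANCOVA) = σ₁²(1 − ρ²)
- Difference = (σ₀ − ρσ₁)², which is never negative and is zero when the slope ρσ₁/σ₀ is 1.

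With equal SDs the ratio ANCOVA/change is (1 + ρ)/2, that is 0.65, 0.75 and 0.85. For a change-score t-test to match ANCOVA on 60 patients it needs 60/0.65 = 92, 60/0.75 = 80 or 60/0.85 = 71 patients.

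**Hand check at ρ = 0.5, equal SDs.** √(2/30) = 0.258.

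- Change: SD = √(2 × 0.5) = 1, SE = 0.258, 0.6/0.258 = 2.32, power ≈ Φ(2.32 − 1.96) = 0.64.
- ANCOVA: SD = √0.75 = 0.866, SE = 0.224, 0.6/0.224 = 2.68, power ≈ Φ(0.72) = 0.76 (0.75 in the simulation, which uses the t distribution and estimates the slope).

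**Simulation of the plan's rule.** 40,000 trials per scenario with bivariate normal data. The t-test on change is replaced by ANCOVA when the baseline t-test has p < 0.05. Both the replacement and, for the scales, the threshold are assumptions, since the plan states neither. Precision lost is 1 − Var(ANCOVA)/Var(rule). Entries are for ρ = 0.3 / 0.5 / 0.7.

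| σ₁/σ₀, n per arm | Power, plan's rule | Power, ANCOVA | Precision lost |
|---|---|---|---|
| 1, 30 | 0.50 / 0.64 / 0.84 | 0.67 / 0.75 / 0.89 | 27% / 19% / 10% |
| 1.25, 30 | 0.57 / 0.70 / 0.89 | 0.66 / 0.74 / 0.89 | 15% / 7% / 0% |
| 1.5, 30 | 0.61 / 0.74 / 0.89 | 0.66 / 0.75 / 0.89 | 8% / 2% / −1% |
| 0.8, 30 | 0.40 / 0.53 / 0.73 | 0.66 / 0.75 / 0.89 | 41% / 35% / 29% |
| 1, 15 | 0.26 / 0.35 / 0.53 | 0.37 / 0.44 / 0.58 | 26% / 18% / 9% |

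The 15-per-arm row is illustrative (one diagnosis, or a subset after motion exclusions); the plan gives no such count.

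**Further results, 30 per arm, equal SDs.**

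- The trigger fires in about 5% of trials, so the rule regains little power over the plain change-score test.
- The rule and ANCOVA give different significance verdicts in 23% / 16% / 7% of trials.
- In about 9% of trials the baseline |t| lies between 1.5 and its critical value of about 2.0, a difference of 0.39 to 0.52 SD. The change score then over-corrects by (1 − ρ) times that difference, on average 0.30 / 0.21 / 0.13 SD. With no treatment effect the rule rejects in 11.5% / 10.3% / 7.3% of these trials, ANCOVA in about 5%.
- Overall type I error of the rule is 0.036 to 0.050 over the SD ratios 0.8, 1 and 1.25, and 0.037 to 0.044 at 15 per arm.
- Hypothesis 3c gate, taking SPS and one ROI contrast as independent (power squared): 0.25 / 0.41 / 0.71 under the rule, against 0.44 / 0.56 / 0.78.

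**The case against.** The strongest reply is that this concerns efficiency, not validity. The change-score t-test is unbiased under randomisation, its overall error rate holds, and the plan provides adjustment for imbalance in every outcome family. That is correct, and the point does not claim otherwise.

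Second, the equal-SD figures may flatter ANCOVA for the scales. Section 2.2 selects on severity ("Moderate or greater severity of sensory phenomena", with minimum Y-BOCS or YGTSS scores), which narrows the baseline spread and makes a larger week-4 SD plausible. The rows for ratios 1.25 and 1.5 then apply, and at ρ = 0.7 the gain is nil. With equal SDs and ρ = 0.9 it is about 2%. This stands as a limit on size. It does not reverse the recommendation: when the slope is near 1, ANCOVA costs at most about 1% to 3% of variance.

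Third, the calculation treats each outcome as one number per patient. If fMRI testing stays voxel-wise with an ROI-mean covariate, the gain is smaller, by an amount not calculated here.

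Fourth, the gate figures assume independence and a single ROI contrast, whereas the plan accepts activation or connectivity, and either severity scale. Correlated outcomes or an easily passed imaging condition would narrow the gap towards the single-test differences of about 0.17 / 0.11 / 0.05. The figures are therefore only illustrative.

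None of this answers the missing statement of which analysis governs.

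**Conclusion.** The concern holds. The plan's default omits a covariate it already has, and its conditional rule rarely brings it back. With 30 per arm and equal SDs the assumed cost is 10% to 27% of precision, or roughly 0.04 to 0.17 in power. The cost is larger if the spread narrows by week 4, and falls to nothing as the baseline slope approaches 1. These sizes rest on assumed correlations, SDs and effect, on 1:1 allocation with about 60 analysed, and on scalar outcomes. The direction does not depend on those values beyond a trivial loss near slope 1. The undefined triggers and the unnamed governing analysis are faults at any correlation. This is an improvement that should be made; it does not invalidate the trial.

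**What to change.** Rewrite Section 4.2 as follows.

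- Delete the baseline pre-tests. Make the primary analysis of each continuous outcome an ANCOVA of change (or of the week-4 value) on treatment, with the same measure's baseline value as covariate, for everyone in the analysis set whatever imbalance is seen.
- Task fMRI: take the covariate from the whole a priori ROI for the same contrast. This is close to the follow-up model already described, with the region fixed and the condition removed.
- Connectivity: define the baseline value or map for the same seed. At present only seed-to-whole-brain maps are specified.
- Analyse Y-BOCS and YGTSS separately, each with its own baseline. Section 4.1 uses different instruments by diagnosis: "tics symptoms in TD patients will be assessed using Yale Global Tic Severity Scale", and Y-BOCS in OCD patients. Add diagnosis as a covariate only where both groups are pooled (SPS, fMRI), with a stated coding for patients who have both.
- State that the ANCOVA result, not the t-test, determines whether Hypotheses 3b and 3c are tested.
- Report models with covariates chosen from observed imbalances only as sensitivity analyses.

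The cost is SAP wording, one added connectivity definition, and one or two degrees of freedom. No new data, visits or patients are needed.
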